NCT04990973

Brief Title: Evaluation of Diet and Sleep in Vascular Health: A Pilot Study

Official Title: Influence of Diet on Sleep and Cardiovascular Risk

Unique Protocol ID: AAAT7042

Date: 03/26/2024

Protocol

The goal of this study is to test the impact of diet on sleep and cardiovascular disease risk factors.

Poor sleep quality is highly prevalent in adults in the U.S. and worldwide. Recent work suggests that dietary intakes may influence sleep. This pilot mechanistic study will test whether consuming a diet aligning with recommendations for a Mediterranean dietary pattern, relative to a typical American diet, improves sleep quality in U.S. adults. Furthermore, we gather preliminary data on whether this diet pattern improves cardiovascular disease risk profile. Given the established relationship between sleep and cardiovascular health.

This pilot study is a randomized, crossover, dietary intervention study with 2 phases: Mediterranean Diet or Average American Diet. Each diet is provided to participants in amounts necessary to maintain baseline body weight given stable activity levels, a requirement of the study; estimated energy needs are computed using the Mifflin St. Jeor equation. During the study, participants are provided 3 isocaloric meals and one snack daily for 4 weeks in each condition. Condition order is randomized by the Biostatistician, and phases are separated by at least 4 week washout. The experimental "Mediterranean Diet" is composed of approximately 40% energy from fat, 20% from protein, and 40% from carbohydrates. The control/comparison diet "Average American Diet" provides 35-37% of energy from fat, 15% from protein, and 48-50% from carbohydrates. Diets differ in fiber content: 40 g/2000 kcal/d for the Mediterranean Diet vs 10 g/2000 kcal/d for the Average American Diet. Participants are not blinded to the intervention.

Prior to enrollment in the study, participants are screened for assessment of health history and current sleep behaviors. Individuals meeting initial eligibility criteria: aged 18-65 y, BMI of 20-34.9 kg/m², sleep complaints, will complete the informed consent process. Those providing consent will continue with screening. Prospective participants are not included if they currently smoke (or quit less than 3 years prior), are diagnosed with a cardiometabolic disease or neurologic disorder, have a psychological or sleep disorder, have gained or lost significant weight in the past 3 months, have allergies to foods included in the study, or are deemed unable to comply with study procedures (either self-expressed or determined by the investigator). Participants also complete a sleep screening; those reporting sleep complaints on the Pittsburgh Sleep Quality Index who also have average total sleep time ≥ 6 h/night based on 2 weeks of daily wrist actigraphy and willing to undergo the interventions post-screening are accrued into the study.

Participants are randomized to the diet for phase 1 at their first baseline visit. At the baseline visit of each phase, measures are collected prior to beginning the corresponding study diet. Following the baseline visit, food is provided by the Bionutrition Unit of the Irving Institute for Clinical and Translational Science at CUMC according to diet allocation. The participants return to the study site every 3-4 days to

collect their study foods over the course of the 4 weeks during each phase. Throughout each phase, sleep is measured daily using wrist actigraphy along with a sleep diary. Fasting blood, overnight urine and fecal samples, and venous endothelial cells are collected at baseline and endpoint of each phase. Participants are instructed to collect all urine from voids occurring after bedtime until the first, next-morning void on the night prior to the first and last study visit of each phase. Tryptophan metabolites and 6-sulfatoxymelatonin are measured from blood and urine samples, respectively. Anthropometric measurements, blood pressure, and heart rate are obtained weekly during each phase. One night of in-home polysomnography is performed in the last week of each phase using a 9-channel portable device (Z-Machine Synergy System, General Sleep Corporation, Cleveland, OH).

Statistical Analysis Plan

Outcome data collected from the study will be assessed for normality using the Shapiro-Wilk test and histograms. Descriptive characteristics for the full sample, and stratified by sex, will be assessed for baseline demographic and sleep data. For continuous variables, means, standard deviations, and ranges will be assessed. For categorical variables, number of participants and corresponding percent of total participants, will be determined. Given the pilot nature of the study and within-person design, analyses of condition effects will be conducted only among those with complete data from both conditions. To assess condition effects, we will use linear mixed models with repeated measures or paired t-tests (for outcomes measured at one time point). Outcomes will be post-baseline values, and each outcome will be tested separately. Participant will be a random effect in the model. Study phase and participant sex will be fixed effects. Models will be adjusted for baseline values of the corresponding outcome measure.

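### The paired t-test for outcomes measured once per phase drops the SAP's own phase term, at a cost in precision or a shifted diet estimate if a phase effect exists

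*Combined protocol and SAP*

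**What the plan says.** The Protocol describes a randomized crossover with two diet phases. On allocation it says "Condition order is randomized by the Biostatistician, and phases are separated by at least 4 week washout", and later "Participants are randomized to the diet for phase 1 at their first baseline visit". It states no allocation ratio, blocking or other balancing of order.

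The Statistical Analysis Plan splits the analysis by how often an outcome is measured: "To assess condition effects, we will use linear mixed models with repeated measures or paired t-tests (for outcomes measured at one time point"). It then adds "Study phase and participant sex will be fixed effects". It restricts the analysis set: "analyses of condition effects will be conducted only among those with complete data from both conditions".

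The SAP does not list which outcomes go to which method. The Protocol's schedule gives the best guide. For polysomnography, "One night of in-home polysomnography is performed in the last week of each phase", and no baseline night is described. For actigraphy, "Throughout each phase, sleep is measured daily using wrist actigraphy along with a sleep diary", which points to the repeated-measures model.

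**The concern.** In a two-period crossover, anything that changes between phase 1 and phase 2 (season, familiarity with the equipment, a general trend in sleep) enters each person's diet difference. Its sign depends on which diet came first. The SAP handles this in its mixed models through the phase term, but a paired t-test cannot.

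The other listed terms are not a problem here. Participant and the main effect of sex cancel in a within-person difference, and there is no polysomnography baseline to adjust for. Phase is therefore the one listed term lost.

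At stake is the polysomnography comparison in a study whose stated aim is sleep quality. The interval may be needlessly wide, or the diet estimate may carry part of the phase effect.

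**Working it through.** **Inputs.** From the documents: two-phase crossover, randomized order with no balancing stated, analysis of completers only, paired t-test for single-time-point outcomes. The documents give no sample size, SD, effect size, phase effect or order split, so there is no planned figure to reproduce. Assumed for illustration: N = 20 completers, two-sided 5% test, no carryover, and a diet effect τ = 0.66 SD, which gives the paired test 80% power with no phase effect. The phase effect π ranges from 0 to 0.5 SD. All SDs are those of the within-person difference within an order group.

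**Model.** Let d be the Mediterranean-minus-American difference and π the phase 2 minus phase 1 effect. Let n1 be the completers with Mediterranean first, n2 those with American first, and N = n1 + n2. Then d has mean τ − π in the first group and τ + π in the second.

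- Paired estimate: expectation τ + π(n2 − n1)/N; variance 1/N for a given split.
- Paired variance estimate: expectation 1 + 4π²n1n2/[N(N − 1)], so the phase effect is counted as error.
- Phase-adjusted estimate: average of the two order-group means of d; expectation τ; SE = 0.5√(1/n1 + 1/n2); N − 2 df.

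**Equal split (10/10).** The two point estimates are identical. At π = 0.5 the expected paired variance is 1 + 4(0.25)(100)/(20 × 19) = 1.263, and √1.263 = 1.12. The exact expected interval widths use the noncentral chi-square with N − 1 df and noncentrality 4π²n1n2/N. They are 1.039 paired and 0.927 adjusted, a ratio of 1.12. At π = 0.25 they are 0.954 and 0.927, a ratio of 1.03.

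| 10/10 | Paired power | Adjusted power | Paired type I error |
|---|---|---|---|
| π = 0.25 | 78% | 80% | 4.4% |
| π = 0.5 | 72% | 80% | 2.9% |

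**Unequal split.** The shift has size π × |n2 − n1|/N:

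- 12/8: 0.25 × 4/20 = 0.05 and 0.5 × 4/20 = 0.10 SD.
- 13/7: 0.25 × 6/20 = 0.075 and 0.5 × 6/20 = 0.15 SD.

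Root mean squared error (RMSE) is √(1/N + shift²) for the paired estimate. For the adjusted estimate it equals the SE above.

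| Split | Paired, π = 0.1 | Paired, π = 0.25 | Paired, π = 0.5 | Adjusted, any π |
|---|---|---|---|---|
| 12/8 | 0.224 | 0.229 | 0.245 | 0.228 |
| 13/7 | 0.226 | 0.236 | 0.269 | 0.234 |

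At π = 0.5, coverage of the paired 95% interval is 97.1% at 10/10, 95.5% at 12/8 and 93.4% at 13/7. Paired type I error at 13/7 is 5.5% (π = 0.25) and 6.6% (π = 0.5). The adjusted test stays at 4.9–5.1% throughout.

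**Where the paired interval becomes the wider one.** This happens above π = 0.08 at 10/10, 0.12 at 11/9, 0.22 at 12/8 and 0.33 at 13/7. Below these values it is slightly narrower but, at an unequal split, centred on the shifted estimate.

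**Averaged over possible splits.** Power, paired against adjusted:

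| Allocation | π = 0 | π = 0.1 | π = 0.25 | π = 0.5 |
|---|---|---|---|---|
| 12/12 randomized, 4 random dropouts | 80.0 vs 79.4% | 79.7 vs 79.5% | 78.0 vs 79.4% | 72.0 vs 79.4% |
| Unrestricted randomization of 20 | 80.0 vs 77.5% | 79.6 vs 77.5% | 77.6 vs 77.5% | 70.7 vs 77.5% |

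A 12/8 split or worse has probability 0.09 under the first scheme and 0.50 under the second.

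**The case against.** The strongest reply is that the harm depends on a phase effect the documents neither report nor exclude. With none, the paired t-test is valid and slightly more powerful. At 0.1 SD it is as good or better. At 0.25 SD under unrestricted randomization the two are level. Averaged over unrestricted randomization the shift is zero and type I error is 5.0%. This is also a pilot. All of that stands, and it limits the point to an improvement in precision plus protection against a shift given the one split that is realised. It does not explain why phase is adjusted for in the mixed models and dropped here.

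A second reply concerns wording. The Protocol says "This pilot study is a randomized, crossover, dietary intervention study with 2 phases: Mediterranean Diet or Average American Diet", and the SAP's sentence on fixed effects names no diet term, so phase could be read as diet. In that case the t-test would lose no listed term. The Protocol's reference to assigning a diet to phase 1 makes the period reading more likely. On the other reading the t-test would still have no period term, and neither would the mixed models, so the remedy would be needed more widely.

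Third, placing polysomnography under the t-test, and actigraphy under the mixed model, is inferred from the schedule. That stands too. The phrase about one time point is undefined. Because outcomes are post-baseline values, the blood, urine, fecal and endothelial-cell measures, with one endpoint value per phase, might also fall under the t-test. Their baseline adjustment, however, points to the mixed model.

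**Conclusion.** The concern holds. The paired t-test cannot carry the phase term that the SAP itself specifies, and the documents offer no balancing of order or other period adjustment in its place. The consequence is conditional. With 20 completers the benefit of adjustment is clear at a phase effect of 0.5 SD: about 7 to 8 points of power at equal or typical splits, and removal of a shift of 0.10 to 0.15 SD at 12/8 or 13/7. Averaged over splits, it is small or nil at 0.25 SD and absent at 0.1 SD. These sizes rest on an assumed sample size, phase effect and split, and on no carryover. The algebra does not depend on them. This change should be made, but the t-test is not invalid in general.

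**What to change.** For every outcome measured once per phase, replace the paired t-test with a model that has diet and phase as fixed effects and participant as a random effect. Equivalently, with complete pairs, take each participant's phase 1 minus phase 2 difference, compare its mean between the two order groups with a two-sample t-test, and halve the contrast. State in the SAP that phase means period, list which outcomes fall under this rule, and report the number of completers in each order.

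The cost is SAP wording and no new data. Statistically it is one degree of freedom plus some variance at unequal splits. With no phase effect and 20 completers, power falls from 80.0% to about 79.8% at 10/10, 78% at 12/8 and 76% at 13/7. Most of the loss at the unequal splits comes from the variance term.

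### Does this pilot need one named sleep variable as the test of its sleep-quality question?

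*Combined protocol and SAP*

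**What the plan says.** The opening of the Protocol poses the question: "This pilot mechanistic study will test whether consuming a diet aligning with recommendations for a Mediterranean dietary pattern". The comparator there is the usual American diet, and the outcome is better sleep quality. It describes the cardiovascular aim more softly, as gathering preliminary data.

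On-diet sleep comes from two arrangements. "Throughout each phase, sleep is measured daily using wrist actigraphy along with a sleep diary", and "One night of in-home polysomnography is performed in the last week of each phase". The Protocol does not say which variable from these sources is the outcome. The specific sleep measures it names are entry criteria: "those reporting sleep complaints on the Pittsburgh Sleep Quality Index who also have average total sleep time" of at least 6 hours are accrued.

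The Statistical Analysis Plan states that "Outcomes will be post-baseline values, and each outcome will be tested separately". Condition effects are assessed with "linear mixed models with repeated measures or paired t-tests (for outcomes measured at one time point"), with participant as a random effect, phase and sex as fixed effects, and adjustment for baseline. It invokes pilot status once, where "Given the pilot nature of the study and within-person design" introduces the restriction to participants who have full data under both diets. It gives no alpha, primary outcome, multiplicity rule or exploratory label.

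**The concern.** Sleep quality is a construct, not a variable. Actigraphy, diary and polysomnography each yield quantities that could stand for it. They also differ in design: actigraphy and the diary run nightly through each phase, whereas polysomnography covers one late night. They could disagree.

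If one sleep variable reached nominal significance and another did not, this document would give no basis for saying whether the hypothesis was supported. The choice could then be made after seeing the results. The softer wording is kept for the cardiovascular aim, so a reader may take sleep as the aim meant to be tested, with a higher false-positive rate than a single nominal 5% test would have.

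**Working it through.** The document gives no alpha, power, sample size or number of outcomes, so it has no figure of its own to reproduce. The check has two parts.

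**1. What the plan leaves open**

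- Actigraphy and diary are recorded daily. The Statistical Analysis Plan takes post-baseline values into a repeated-measures mixed model, so nightly values can enter directly. A nightly summary is not required, although weekly or phase means are not excluded.
- Polysomnography is one night per phase, which points to the paired t-test. There is nothing to summarise across nights.
- Once a variable is chosen, the type of analysis therefore largely follows. What remains open is which variable answers the question.

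**2. Illustrative error rate**

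Assumptions, none from the document: two-sided alpha of 0.05 per test, no true effect, equicorrelated normal test statistics, and a rule that any one significant sleep result supports the hypothesis. Take k = 2 as one actigraphy and one polysomnography variable. Take k = 3 as adding a diary variable, which the document does not say will be tested.

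For independent tests, the chance of at least one false positive is 1 − (1 − 0.05)^k:

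- k = 1: 0.05
- k = 2: 1 − 0.95² = 0.0975
- k = 3: 1 − 0.95³ = 0.1426

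For correlation ρ, it is 1 − ∫ φ(u) [Φ((1.96 − √ρ·u)/√(1 − ρ)) − Φ((−1.96 − √ρ·u)/√(1 − ρ))]^k du, integrated numerically:

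| | ρ = 0 | ρ = 0.5 | ρ = 0.8 | ρ = 0.9 |
|---|---|---|---|---|
| k = 2, any direction | 0.0975 | 0.0907 | 0.0781 | 0.0704 |
| k = 3, any direction | 0.1426 | 0.1254 | 0.0982 | 0.0836 |
| k = 2, favourable direction | 0.0494 | 0.0454 | 0.0390 | 0.0352 |
| k = 3, favourable direction | 0.0731 | 0.0627 | 0.0491 | 0.0418 |

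The single-test references are 0.05 (any direction) and 0.025 (favourable direction). In any direction the ratio runs from 0.0704/0.05 = 1.4 to 0.1426/0.05 = 2.9. Paired t-tests simulated with an assumed 15 complete pairs give similar rates: 0.099 to 0.071 for k = 2 and 0.140 to 0.086 for k = 3 (ρ from 0 to 0.9).

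These values of k count sources, not variables, so they bound nothing. Ten tests would give 1 − 0.95¹⁰ = 0.401 if independent, and about 0.172 at ρ = 0.8. The answer is set by the assumed inputs, not by anything in the plan.

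The separate tests are not invalidated by this. Each keeps its own nominal level. A reader shown three sleep results can hold each to 0.05/3 = 0.0167, which gives 1 − (1 − 0.0167)³ = 0.049 for independent tests.

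**The case for a change.** The strongest case for acting is that the remedy is cheap. One paragraph would name a sleep variable, or one sentence would recast the aim as estimation, with no new data. Pilot status does not fully answer the concern, because the Statistical Analysis Plan uses it only to justify the complete-data restriction. Participants also know which diet they are eating, so it matters whether a diary or a device carries the claim.

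The textual part stands: no on-diet sleep variable is named, and nothing is labelled exploratory. Three things limit its weight.

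- The word pilot sits in the sentence that poses the sleep question, and it recurs in the title and the design description. The Statistical Analysis Plan belongs to the same document and need not repeat it.
- The document does not say which variable should be named. Making one a 5% test would turn a pilot with no stated sample size or power into a confirmatory exercise. Real effects on other sleep variables would be demoted, and using all nights could dilute an effect that appears only late in the 4 weeks. That is a trade-off, not the repair of an error.
- Rewording the aim as estimation, or adding an exploratory label, leaves every analysis and result as it was.

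The worry about choosing after the fact also goes further than this document can show. It carries a registry number, and an outcome may be designated in that record, which was not available here.

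**Conclusion.** The gap is real but descriptive, and no change to the plan follows. This document does not say which sleep variable answers its sleep-quality question. It also does not say that one significant sleep result would settle that question, and it states no confirmatory criterion that could be breached. None of the separate analyses is shown to be wrong.

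The rise from 5% to between 7.0% and 14.3% for two or three tests is an illustration only. It rests on an assumed alpha, test count, correlation and decision rule, and the top of the range needs three independent tests, one of them on a diary variable the plan never lists. Independence is implausible for actigraphy and diary data from the same nights. Analysts can fill the gap sensibly by reporting all sleep outcomes together as pilot estimates with intervals and not singling out one as confirmation.

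### For outcomes measured nightly or weekly, the SAP states only a participant random effect and no averaging rule; if values are entered singly, the diet standard error can be too small.

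*Combined protocol and SAP*

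**What the plan says.** The Protocol section describes a two-phase crossover with 4 weeks on each diet and a washout of at least 4 weeks. It then sets the measurement schedule: "Throughout each phase, sleep is measured daily using wrist actigraphy along with a sleep diary", and "Anthropometric measurements, blood pressure, and heart rate are obtained weekly during each phase". That is up to about 28 nightly or 4 weekly values per participant per phase.

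The Statistical Analysis Plan section says: "To assess condition effects, we will use linear mixed models with repeated measures or paired t-tests (for outcomes measured at one time point". The response is the set of post-baseline values, with each outcome tested separately. The model terms are given in three sentences. The one on random effects reads "Participant will be a random effect in the model". The next, which lists the fixed terms and leaves out diet, reads "Study phase and participant sex will be fixed effects". The last deals with covariates: "Models will be adjusted for baseline values of the corresponding outcome measure".

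Neither section says whether nights or weeks are averaged within a phase, which residual covariance is fitted, whether phase is nested within participant, or how degrees of freedom are obtained. The one actigraphy average that is stated, "average total sleep time ≥ 6 h/night based on 2 weeks of daily wrist actigraphy", is an eligibility rule and not an analysis rule.

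**The concern.** A participant eats one diet throughout a phase. However many nights are recorded, that participant contributes one difference between diets, and the error that matters for it is how much a person's level varies from one phase to the other. With single nights entered and only a participant intercept, the model judges the diet effect mainly against night-to-night scatter and treats each night as fresh evidence about diet.

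The fixed phase effect removes a shift shared by all participants. It does not remove shifts that differ between participants, such as individual workload, the season in which each person was enrolled, or individual response to diet. Phases at least 8 weeks apart from start to start (4 weeks of diet plus at least 4 of washout) leave room for such shifts.

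The trial asks whether the Mediterranean diet improves sleep quality, and actigraphy and diary are its nightly sleep measures. Intervals that are too narrow could carry a chance difference between participants' phases into later work as a diet signal.

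**Working it through.** The plan states no sample size, power, alpha or variance, so there is no figure of its own to reproduce. The check asks how far the standard error from the literal model departs from the true one.

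**Inputs from the documents.** Two phases; 4 weeks per phase, so m = 28 nights or m = 4 weekly values; participant random; phase and sex fixed.

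**Assumptions.** n = 20 with equal sequences; two-sided 5% test at 1.96; diet included as a fixed effect, since the SAP paragraph exists to assess condition effects; no baseline covariate at first.

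**Set-up.** Scale within-person variance to 1. Let g be the share due to participant-by-phase shifts and 1 − g the night-to-night (or week-to-week) part, serially independent at first.

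- True variance of the diet estimate: (2/n) × T, with T = g + (1 − g)/m.
- Variance reported by the participant-intercept model: (2/n) × M, with M = R/m and R the expected residual mean square, R = (1 − g) + g × m(n − 2)/(2nm − n − 2).
- Residual degrees of freedom, 28 nights: 2 × 20 × 28 − 20 − 2 = 1,098. The diet contrast itself has n − 2 = 18.
- Multiplier of g in R: 28 × 18/1,098 = 0.459 for nights; 4 × 18/138 = 0.522 for weeks.
- Ratio of true to reported SE: r = √(T/M). Actual type I error: P(|Z| > 1.96/r).

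**Worked case, 28 nights, g = 0.05.** T = 0.05 + 0.95/28 = 0.0839. R = 0.95 + 0.05 × 0.459 = 0.973, so M = 0.973/28 = 0.0347. r = √(0.0839/0.0347) = 1.55. P(|Z| > 1.26) = 21%. A nominal 95% interval covers about 79%.

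| Values per phase | Share g | T | M | r | Type I error |
|---|---|---|---|---|---|
| 28 | 0 | 0.0357 | 0.0357 | 1.00 | 5% |
| 28 | 2% | 0.0550 | 0.0353 | 1.25 | 12% |
| 28 | 5% | 0.0839 | 0.0347 | 1.55 | 21% |
| 28 | 10% | 0.1321 | 0.0338 | 1.98 | 32% |
| 4 | 5% | 0.2875 | 0.2440 | 1.09 | 7% |
| 4 | 10% | 0.3250 | 0.2380 | 1.17 | 9% |
| 4 | 20% | 0.4000 | 0.2261 | 1.33 | 14% |

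Simulation agrees: about 11%, 21% and 33% for nights at shares of 2%, 5% and 10%, and about 10% and 14% for weeks at shares of 10% and 20%. The assumed n hardly matters: at g = 0.05 with 28 nights, the formula gives 21% for n = 12 and for n = 30.

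**Serial correlation alone (g = 0, 28 nights).** Replace T by V/m, where V = 1 + 2Σ(1 − k/m)ρ^k, and R by [2n(m − V) + (n − 2)V]/(2nm − n − 2).

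| Lag-1 ρ | V | r | Type I error |
|---|---|---|---|
| 0.2 | 1.478 | 1.22 | 11% |
| 0.3 | 1.813 | 1.36 | 15% |
| −0.1 | 0.824 | 0.91 | 3% |

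Only positive correlation makes the standard error too small.

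**Does something already in the plan prevent this?**

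- *Fixed phase effect.* A shift common to everyone, of 0.25 to 1.0 within-person SD, left simulated type I error at 4.8% to 5.3%. Only individual shifts matter.
- *Baseline adjustment.* The only pre-diet actigraphy spelled out is the screening record. Used as baseline, it is the same in both phases and cancels from the diet contrast: 31% at a 10% share. The Protocol section also says "At the baseline visit of each phase, measures are collected prior to beginning the corresponding study diet", so a phase-specific baseline is possible. With a phase-specific 14-night mean, the figure at a 10% share was 19%; with a single value, 29%. Adjustment reduces the excess but does not remove it.
- *AR(1) residual plus participant intercept.* 11%, 23% and 31% at shares of 2%, 5% and 10%; 6% with lag-1 0.2 and no share. It handles serial correlation, not participant-by-phase variation.

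**After the fix.** One mean per participant per phase, tested on 18 degrees of freedom, gave 4.6% to 5.2% in 20,000-run simulations of nine settings: 28 nights at shares of 0, 2%, 5% and 10%; 4 weeks at 10% and 20%; lag-1 0.2, 0.3 and −0.1. A nested phase intercept with Satterthwaite degrees of freedom gave 3.1% to 6.0% over a wider set of settings.

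**The case against.** The strongest reply is that this rests on silence. The SAP's list of model terms is plainly a summary: it does not even name condition. It calls participant a random effect, not the only one. Its reference to repeated measures may imply a residual covariance that the authors saw no need to name. It may also mean simply the two phases with one post-baseline value each, and then a participant random effect is enough. Harm needs single values to be entered, no term that absorbs the dependence, and real participant-by-phase variation or positive serial correlation. The documents establish none of these. This is also a pilot with no stated alpha.

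Most of that stands as a limit on the claim. A reader might infer that the SAP prescribes independent nights and is therefore wrong as written; it does not go that far. Nor does serial correlation of any sign understate the error, since a negative correlation does the reverse.

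The reply does not close the gap. The SAP separates outcomes measured once from the rest, and nightly and weekly series are the clearest cases of the rest, so entering values singly is a natural reading. An unnamed covariance may also be one that does not help, as the AR(1) result shows. Pilot status lowers the stakes, but the Protocol section still says that the study will test whether the diet improves sleep quality.

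**Conclusion.** The point holds conditionally and should be fixed. On a reading that the SAP leaves open, the diet standard error is too small for nightly actigraphy and diary outcomes, and modestly so for weekly blood pressure, heart rate and anthropometrics. Polysomnography (one night per phase) and the blood, urine, fecal and endothelial samples (one post-baseline value per phase) are unaffected. So is any outcome averaged to one value per phase.

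Every size depends on assumed values of n, test level, variance share and correlation, because the documents give none. A reader might infer that the trial's sleep results will have a false-positive rate of 21% or 33%. The documents do not support that: they show neither that values enter singly nor how large the participant-by-phase share is. They support the narrower statement that a share as small as 2% would roughly double the nominal error for 28 single nights, and that nothing written in the plan rules this out. Confidence is medium. How a phase-specific baseline should be parameterised is a separate question and forms no part of this point.

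**What to change.** Add one or two sentences to the Statistical Analysis Plan section. For any outcome with more than one post-baseline value per phase, state that one mean per participant per phase is analysed in the crossover model, with condition, phase, sex and baseline fixed and participant random. If single values are to be used instead, add a random intercept for phase within participant and name Kenward-Roger or Satterthwaite degrees of freedom. Do not rely on an AR(1) residual or on baseline adjustment alone. If the analysis has already been run, the report should say which form was used.

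No new data are needed. The cost is wider intervals. Where there is neither participant-by-phase variation nor serial correlation, the widening buys nothing and is about 7% at n = 20: the critical value rises from 1.96 to 2.10 on 18 degrees of freedom, and 2.10/1.96 = 1.07. The nested model can then be slightly conservative, with type I error of about 3% to 5%.
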